9.3.4 Subjective Safety and Tolerability Measures

Treatment adherence. Patients will self-report adherence in the study questionnaires. Compliance will also be measured by pill counts performed every 3 months. The number of pills taken out of the total prescribed in a 3-month period will be modeled as a random effects binomial regression model.¹²⁶ The binomial rates from 8 time points (month 3 to 24) will be modeled as unstructured mean model with 7 indicator variables as well as polynomial models over time. The random-intercept and the random intercept and slope models will be considered. The significance of the time indicators or parameters by treatment interaction will be evaluated for treatment difference in compliance.

Voluntary withdrawals will be examined at the end of the study by comparing the percent of withdrawals between the treatment groups using a chi-square test or Fisher's exact test.

Patient reported symptoms. The outcomes will be scored as a 5-point Likert-type scale (0 to 4) in response to questions on how much the patients are bothered by certain symptoms. The questionnaire will be administered at Days 0, 14, 42 and 90, and every three months after Day 90, for a total of eleven time points. The responses will be treated as normally distributed, as ordinal or dichotomized variable, and we will apply the linear mixed effects model or generalized linear mixed effects model methods to compare changes between treatment groups. Because of additional time points available, in addition to the unstructured mean model, we will also fit piecewise models with join point at 6 months, considering linear and curvilinear trajectories between 6 m and 24 m time points.

Aim 1.2.2: To examine the modifying effects of demographic, clinical, and molecular characteristics on both efficacy and safety markers.

As the primary aim of this trial is to examine the main effects of low-dose carvedilol on LV-TD z-score, we will examine the modifying effects of demographic, clinical, and molecular characteristics as exploratory analysis. Even if time by treatment interaction (main treatment effect) is not significant, examining the modifying effects of covariates may reveal subgroups that respond differently to carvedilol. A three-way interaction of time by treatment by modifying variable will be included in the longitudinal model containing a two-way time by treatment group interaction. Modifying effects will be considered statistically significant if the three-way interaction is significant. The covariates of interest are described below.

A. Patient demographics

The following variables are known to affect HF risk and LV T-D.

Attained age – continuous, time-varying variable.

Body mass index (BMI) – continuous, time-varying variable. It will also be grouped into ordinal categories: underweight (<19), normal weight (19-24), overweight (25-29), obese (30-39), morbidly obese (40+).

Cardiovascular disease – coronary artery disease (angina, acute myocardial infarction, coronary artery bypass graft surgery [CABG], percutaneous coronary intervention), ventricular or atrial arrhythmias, cerebrovascular disease, congenital heart lesions.

CV risk factors – Hypertension, dyslipidemia, diabetes, renal insufficiency, chronic lung disease, thyroid disorder, smoking history (includes smoking status, and if quit, date of cessation). All CV risk factors will be recorded as dichotomous variables (present/absent), with recording of date of onset.

Family history of cardiovascular disease – dichotomous (yes/no), constant over the study period. Outcomes of interest will include: sudden cardiac death, conduction system disease, cardiomyopathy, and coronary artery disease (CAD). For the CAD, we will also examine the frequency of the following classifications: 0 = no direct blood relatives (parents, siblings) with CAD; 1 = one or more with CAD at age ≥ 55 years for male relatives or ≥ 65 years for female relatives; 2 = one or more with CAD at age less than 55 years for male relatives or less than 65 years for female relatives.

B. Clinical treatment characteristics.

The following variables are known to influence HF risk among childhood cancer survivors.

Chest radiation – continuous, time-invariant. We will also dichotomize per the stratification factor for randomization.

Age at exposure to anthracyclines – continuous, time-invariant. We will also categorize per the stratification factor for randomization.

Latency from radiation therapy – continuous, time-varying. We will examine if intervention effects vary by time since exposure to therapeutic radiation.

C. Molecular characteristics

The following variables are known to influence efficacy of carvedilol in the treatment of HF patients and will be analyzed at a later date.

CYP variants – dichotomous (yes/no), constant over the study period

$\beta_{1, 2}$ and α_1 -Adrenergic receptor and Norepinephrine transporter variants ([Section 2.5](#)) – dichotomous (yes/no), constant over the study period.

In addition to testing their significance as effect modifiers, we will also examine their relationship with the outcome variables (LV T-D, ESWS, Natriuretic peptides, MPI etc.) to validate known relationships. Proc Mixed for normal data and Proc GLMMIX for non-normal data in SAS 9.1 (Cary, North Carolina) will be used for analysis.

9.3.5 Exploratory Aim 1.3:

To evaluate the long-term efficacy of carvedilol in preventing cardiomyopathy and/or heart failure in high-risk childhood cancer survivors.

For this exploratory aim, long term overall and cardiac health status will be described for study participants and as exploratory analyses compared between the 2 study arms.. The majority of these childhood cancer survivors are expected to be in active follow-up and routine clinical information (including annual echocardiograms) is already being collected as part of the patients' standard care. In support of this aim, ascertainment of basic information regarding overall and cardiac health status: vital status, development of cardiomyopathy/heart failure, most recent ejection fraction and shortening fraction data in order to determine if there has been a cardiac event (as defined in [Section 8.1.1](#)) for up to 5 years after study enrollment.

9.4 **Power and Sample Size**

Primary Aim - Determine the impact of a two-year course of carvedilol on LV T-D:

For sample size calculation, we let Y, the response, be the z-score expected for LV T-D in both groups. Because of randomization, we expect no difference between the expected values of Y at t0 between treatments. However, if the intervention is efficacious, we expect the linear slopes of the two groups to diverge over time, with no significant change in the slope of LV T-D for the carvedilol arm. Power/sample size calculation was conducted by assuming a linear change in LV T-D z-score over time. With this assumption, longitudinal power calculation requires specification of the following: 1) expected values of Y at t0 the carvedilol and control arms, 2) the expected difference in Y at 24 months between the two arms, and 3) the correlations between the repeated measurements over time. These were obtained from the following sources: **1) Expected baseline value of LV T-D** was derived from a cross-sectional study evaluating cardiac function in 150 long-term survivors of childhood cancer treated with anthracyclines at City of Hope (median age at evaluation, 24.2 years, time since diagnosis 12.5 years).¹²⁷ Mean LV T-D z-score for survivors exposed to HD-anthracycline (≥ 250 mg/m²) was -0.72 (SD 1.0), compared to -0.03 (SD 1.1) in those treated with lower doses (< 250 mg/m²); $p < 0.05$.¹²⁷ **2) Projected decline in LV T-**

D between baseline and 24 months was derived from two clinical trials^{21,128} These studies were selected because they provided reliable longitudinal data of cardiac function, obtained from multi-institutional clinical trials that used a centralized core echo lab. Patients treated with higher dose anthracyclines had a decline in LV T-D Z-score of approximately 0.2/year, providing us with an estimated rate of LV-TD decline for the placebo arm of the current study. Given these findings, we project that mean LV T-D z-score will be -0.7 at baseline for both arms of the trial, mean LV T-D z-score for the placebo arm will decline to -1.1 at the end of the 2-year intervention, and there will be preservation of LV T-D z-score for the carvedilol arm, resulting in a projected difference at 24 months between the two arms of 0.4. We acknowledge the possibility that instead of preservation of LV T-D, there could be further decline in LV T-D for the carvedilol arm, decreasing the observed effect size at 24 months to < 0.4.

ACTIVATION PROTOCOL:

However, as discussed below, the current trial will have adequate power to detect prevention effects that are 12.5% to 37.5% lower than the projected differences between carvedilol and placebo arms. **3) Correlation between measurements over time** was based on

Table 3. Detectable differences in endpoints by correlation estimates
Sample size: 125/arm; Attrition: 15%/yr; Power: 0.8; Type I error: 0.05

Endpoint	Baseline	Estimated SD	Correl. Between measurements		
	Value		0.6	0.7	0.8
Primary					
LV T-D (Z)	-0.7	1.0	0.32	0.28	0.23
Secondary					
LVEDV (mL)	105.7	26.9	8.6	7.5	6.2
LVESV (mL)	45.0	11.7	3.7	3.3	2.7
LVEF (%)	60.0	5.0	1.6	1.4	1.2

preliminary data examining LV T-D values for the 40 patients enrolled onto the clinical trial not through this COG study but through a different mechanism with at least a baseline and six month time point; the correlation between these two time points was 0.7. Since we do not know what the correlation will be after 2 years, Table 3 depicts detectable differences for correlations ranging from 0.6 to 0.8. In addition, we show detectable differences for important secondary endpoints such as: EF, LVEDV, LVESV. Of note, as in LV T-D, estimated baseline mean values for these echocardiographic endpoints and their standard deviations were derived from our recently completed study evaluating cardiac function in comparable survivors of childhood cancer,¹²⁷ as well as from patients currently enrolled on the clinical trial. Correlation between measurements over time (baseline to 6 months) for these indices ranged from 0.6 (EF) to 0.8 (LVEDV, LVESV).

The longitudinal power calculations were conducted using the program RMASS2.¹²⁹ We assumed a Type I error of 0.05, power of 0.80, 2-sided test, linear trend, and compound symmetry correlation matrix ([ρ] ranging from 0.6 to 0.8). An attrition rate of 15% per arm/year (voluntary withdrawal, discontinuation due to drug intolerance, unexpected events [pregnancy/ relapse]) was assumed, taking into consideration the observed attrition rate (13%/year) in the study to date. Table 3 shows the minimum effect size at 24 months that can be detected for a given correlation between measures. For example, with 125 individuals in each group, we have 80% power to detect a difference of at least 0.32 in LV T-D z-score between the two arms if the correlation between baseline and the 2 year LV T-D z-score is 0.6. Thus, if the absolute difference between the carvedilol and placebo arms is smaller than 0.4, the current sample size will still be sufficiently powered to detect a lower degree of remodeling prevention. With regards to the secondary endpoints of efficacy, 3-6 mL increases in LVESV, 6-10 mL increases in LVEDV, or 3-5% drops in LV

EF (from normal resting LV EF) have been associated with adverse cardiovascular outcomes in clinical trials with patients with preserved or mildly depressed EF.¹³⁰⁻¹³² Thus, effect sizes presented in Table 3 are plausible and clinically meaningful.

WITH AMENDMENT #4:

As discussed below, the current trial will have adequate power to detect prevention effects that are 8.5% to 52.5% lower than the projected differences between carvedilol and placebo arms. **3) Correlation between measurements over time** was based on preliminary data examining LV T-D values for the 40 patients enrolled onto the clinical trial not through this COG study but through a different mechanism with at least a baseline and six month time point; the correlation between these two time points was 0.7. Since we do not know what the correlation will be after 2 years, Table 4 depicts detectable differences for correlations ranging from 0.6 to 0.9. In addition, we show detectable differences for important secondary endpoints such as: EF, LVEDV, LVESV. Of note, as in LV T-D, estimated baseline mean values for these echocardiographic endpoints and their standard deviations were derived from our recently completed study evaluating cardiac function in comparable survivors of childhood cancer,¹²⁷ as well as from patients currently enrolled on the clinical trial. Correlation between measurements over time (baseline to 6 months) for these indices ranged from 0.6 (EF) to 0.9 (LVEDV, LVESV).

Table 4. Detectable differences in endpoints by correlation estimates						
Sample size: 91/arm; Attrition: 19%/yr; Power: 0.8; Type I error: 0.05						
Endpoint	Baseline		Correl. Between measurements			
	Value	Estimated SD	0.6	0.7	0.8	0.9
Primary						
LV T-D (Z)	-0.7	1	0.38	0.34	0.28	0.21
Secondary						
LVEDV (ml)	105.7	26.9	10.2	9.1	7.5	5.6
LVESV (ml)	45	11.7	4.4	4	3.3	2.5
LVEF (%)	60	5	1.9	1.7	1.4	1.1

The longitudinal power calculations were conducted using the program RMASS2.¹²⁹ We assumed a Type I error of 0.05, power of 0.80, 2-sided test, linear trend, and compound symmetry correlation matrix ($[\rho]$ ranging from 0.6 to 0.9). An attrition rate of 19% per arm/year (voluntary withdrawal, discontinuation due to drug intolerance, unexpected events [pregnancy/ relapse]) was assumed. Table 4 shows the minimum effect size at 24 months that can be detected for a given correlation between measures. For example, with 91 individuals in each group, we have 80% power to detect a difference of at least 0.38 in LV T-D z-score between the two arms if the correlation between baseline and the 2 year LV T-D z-score is 0.6. With regards to the secondary endpoints of efficacy, 3-6 mL increases in LVESV, 6-10 mL increases in LVEDV, or 3-5% drops in LV EF (from normal resting LV EF) have been associated with adverse cardiovascular outcomes in clinical trials with patients with preserved or mildly depressed EF.¹³⁰⁻¹³² Thus, effect sizes presented in Table 4 are plausible and clinically meaningful.

Secondary Aim – Establish safety and tolerability of the two-year course of carvedilol.

ACTIVATION PROTOCOL:

Adverse events: We assume the rate of Grade 2-4 toxicities in the placebo group to be low, at 5%. At the end of the study, assuming 88 individuals remaining in each arm (15% attrition/year from the original 125/ arm), the study will have at least 80% power to detect

an adverse event rate of 19.2% in the carvedilol group based on Fisher's exact test and Type I error=0.05.

Adherence to therapy: We will examine the difference in adherence rates by comparing the percent adherence by treatment group. With 125 study participants at baseline per arm, assuming a constant adherence rate of 90% in the placebo group, a between-measurement correlation of 0.6, 15% yearly attrition, and 2-sided alternative, there will be 80% power to detect an adherence rate of 75% in the carvedilol group.

Voluntary withdrawals: We assume that the proportion of patients in the placebo arm who will withdraw voluntarily by 24 months is 20% (10%/year); of note, this is less than the assumed overall attrition rate of 15%/year because attrition could occur due to other reasons such as toxicities, cancer recurrence, etc. With 125 patients in each arm at baseline, using Type I error=0.05, the study will have 80% power to detect a >15% absolute difference in the voluntary withdrawal rates between the two study arms.

WITH AMENDMENT #4:

Adverse events: We assume the rate of Grade 2-4 toxicities in the placebo group to be low, at 5%. At the end of the study, assuming 56 individuals remaining in each arm (19% attrition/year from the 91/arm at baseline), the study will have at least 80% power to detect an adverse event rate of 24.7% in the carvedilol group based on Fisher's exact test and Type I error=0.05.

Adherence to therapy: We will examine the difference in adherence rates by comparing the percent adherence by treatment group. With 91 study participants at baseline per arm, assuming a constant adherence rate of 90% in the placebo group, a between-measurement correlation of 0.6, 19% yearly attrition, and 2-sided alternative, there will be 80% power to detect an adherence rate of $\leq 70\%$ in the carvedilol group.

Voluntary withdrawals: We assume that the proportion of patients in the placebo arm who will withdraw voluntarily by 24 months is 26% (13%/year); of note, this is less than the assumed overall attrition rate of 19%/year because attrition could occur due to other reasons such as toxicities, cancer recurrence, etc. With 91 patients in each arm at baseline, using Type I error=0.05, the study will have 80% power to detect a >21% absolute difference in the voluntary withdrawal rates between the two study arms.

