1.2 Secondary Aims

1.2.1 To establish safety and tolerability of this two-year course of low-dose carvedilol, assessing both objective measures (hepatic function) and patient reported outcomes.

1.2.2 To examine the modifying effect of demographic, clinical, and molecular characteristics on the risk: benefit ratio from this two-year carvedilol intervention.

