2.7 Hypotheses

We hypothesize that carvedilol delivered at a dose of 12.5 mg per day for two years will be an efficacious and safe option for HF risk reduction in childhood cancer survivors at very high risk of developing HF due to previous exposure to high-dose anthracyclines. We also hypothesize that there exists a subgroup within the patient population who will derive the most benefit from taking carvedilol for HF prevention with least risk.

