4.3 Dose Escalation and Up-Titration Period

The goal of the up-titration period is to reach the highest dose level that will be continued throughout the maintenance phase. After enrollment and randomization, all subjects will be entered into the up-titration period, during which they will receive carvedilol or placebo. The first dose of the double-blind medication will be administered with food at the clinic. At one- and two- hours after administration of the dose, heart rate and blood pressure will be assessed. The first titration of carvedilol (or matched placebo) will occur two weeks following randomization (± 2 calendar days), with the subsequent titration occurring four weeks later (± 7 calendar days). The initial daily dose will be 3.125 mg once daily. The target final titration dose will be 6.25 mg twice daily (BID) (standard schedule, carvedilol dosing).

The titration dose levels of carvedilol or matched placebo are:

Level	Dose	Frequency
1	3.125 mg	once daily (QD)
2	6.25 mg	once daily (QD)
3	6.25 mg	twice daily (BID)

During the up-titration from level 1 to 2, subjects will be instructed to not take their usual dose of the study medication the morning of their study visit. This dose will be given in clinic, after visit assessments have been completed.

For titration from level 2 to 3, subjects will be instructed to take their daily carvedilol dose the evening prior to their clinic visit, and to refrain from taking the study medication the morning of their study visit. This dose will be given in clinic, after visit assessments have been completed.

At each up-titration visit, the following parameters will be assessed:

- Interim history and physical examination (except Day 0).
- Sitting pre-dose blood pressure and heart rate.
- Sitting 1- and 2-hour post-dose blood pressure and heart rate.
- Concomitant medication assessment.
- Study medication compliance using the Adherence Tracking Form (except Day 0).
- Investigator's assessment of subject's ability to tolerate the study medication, including acute tolerability for at least 2 hours after the first dose of each up-titration level.

If the dose level is judged by the investigator to be tolerated based on the criteria in [Section 4.3.1](#), the dose of carvedilol or matching placebo will be increased to the next level.

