4.3.1 Criteria for Assessment of Drug Tolerability Prior to Dose Escalation

The goal of the up-titration period is to reach the highest dose level that will be continued throughout the maintenance phase. Subjects who are unable to tolerate escalation from dose level 1 to 2 (Day 14) will go off protocol therapy. Subjects at dose level 2 will be escalated to dose level 3 or maintained at level 2, depending on tolerability. Dose tolerability will be determined following administration of study drug in clinic. Symptoms will be monitored for a minimum of 2 hours post medication administration. Individuals who meet the following criteria at the end of the evaluation period will be deemed ineligible for dose escalation:

- Low resting systolic blood pressure: < 90 mmHg.
- Bradycardia: heart rate < 50 BPM.
- Sustained or symptomatic ventricular dysrhythmia. Significant conduction defects (i.e. second or third degree atrio-ventricular block) on ECG.
- Dizziness: moderate unsteadiness or sensation of movement (Grade 2 toxicity).
- Flushing: moderate symptoms, limiting instrumental ADL (Grade 2 toxicity).
- Other reasons not listed above, but deemed related to study drug per the investigator.

Prior to escalation to the next dose level, investigators will complete a Dose Escalation Form, confirming that the individual did not demonstrate any of the above signs or symptoms.

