4.3.3 Subjects on Dose Level 2 (6.25 mg/Placebo Daily)

Four weeks following escalation from dose level 1 to 2, subjects will return to clinic for a clinical evaluation. During that visit, there will be two options:

- Increase to dose level 3, *or*
- Maintain at the current dose level if dose escalation is considered inadvisable by the investigator.

Individuals on dose level 2 who are unable to tolerate dose escalation to level 3 have the option to return in 2 weeks, where there will be another attempt at dose escalation. If at that time, dose escalation is not considered advisable by the investigator, then subjects will remain on dose level 2 for the duration of the study. For these individuals, dose level 2 will be considered the fixed maintenance dose.

4.4 **Maintenance Period**

At the completion of the up-titration period, subjects will enter the maintenance phase of the study which will last 24 months from the first dose of study drug. For the purposes of this study, the initial maintenance visit will be synonymous with the “end of up-titration” visit. Subjects will enter the maintenance phase receiving the highest dose of study medication that was tolerated in the up-titration phase. This may be dose level 2 or 3.

During the maintenance period, study visits will be scheduled on 90, 180, 365, 540, and 730 days. These study visits may occur within +/- 10 business days of the calculated visit day. Additional visits may be scheduled by the investigator, as appropriate, based on clinical indication. The study CRA/CRN will follow-up with a telephone call in between clinic visits, as outlined below.

4.5 **Follow-up Visits**

Study participants will be asked to return their pill kits on Day 90 for a pill count, refill of the medication, and clinical evaluation; patient reported symptoms will be accessed via a standardized Symptom Log (see study web page on the COG website). For the Day 90 visit only, the patient has the option to do an in-person visit or a phone follow up, depending on their ability to easily return to the clinic.

Subsequent return clinic visits will occur on Days 180, 365, 540 and 730 following randomization. The following parameters will be assessed according to the study observations (see [Section 7.1](#)).

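### No planned analysis uses the dose level reached, so a patient held at half the target dose counts as fully adherent, fully treated and not withdrawn

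*Combined protocol and SAP*

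**What the plan says.** The hypothesis in Section 2.7 concerns "carvedilol delivered at a dose of 12.5 mg per day for two years". Section 4.3 sets three levels: 3.125 mg once daily, 6.25 mg once daily, and 6.25 mg twice daily as the target.

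Not everyone is expected to reach the target. Section 4.3.1 states: "Subjects at dose level 2 will be escalated to dose level 3 or maintained at level 2, depending on tolerability". Section 4.3.3 allows a second attempt two weeks later. If that is also judged inadvisable, "then subjects will remain on dose level 2 for the duration of the study", and "For these individuals, dose level 2 will be considered the fixed maintenance dose". Patients who cannot go from level 1 to level 2 are taken off protocol therapy (Sections 4.3.1 and 8.1).

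The secondary aim (Section 1.2.1) is: "To establish safety and tolerability of this two-year course of low-dose carvedilol". The analyses that serve it are:

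- Section 9.3.3: Grade 2-4 toxicities by arm (Fisher's exact test), and liver function.
- Section 9.3.4: adherence ("The number of pills taken out of the total prescribed in a 3-month period will be modeled"), voluntary withdrawals by arm, and patient-reported symptoms at eleven time points that include Days 0, 14, 42 and 90.

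Section 10.7 defines compliance as tablets dispensed minus tablets returned, divided by tablets prescribed per day times days since the last visit. The as-treated analysis in Section 9.3.1 replaces the arm indicator with a pill-count rate: 0 for placebo, between 0 and 1 for carvedilol.

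**The concern.** Every exposure measure in the plan is relative to the prescribed dose, and the prescribed dose is itself lowered when a patient does not tolerate escalation. The event that shows intolerance of the target dose therefore resets the yardstick by which tolerability is judged. No analysis in Section 9.3, including the effect-modifier analyses, uses the level reached.

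Two conclusions are at stake. For Aim 1.2.1, similar adherence and similar withdrawal rates could be reported although the arms differ in how many patients could take the target dose. For efficacy, a null or small LV T-D effect could not be read against the dose delivered, and the as-treated analysis, which is meant to account for actual uptake, would enter half-dose patients at full exposure.

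**Working it through.** **1. Level 2 under the plan's own formula.** Inputs: the levels in Section 4.3 and the compliance formula in Section 10.7. Take 90 days with every dose taken, assuming one 6.25 mg capsule per dose.

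- Level 3: 180 / (2 × 90) = 100%; delivered 180 × 6.25 = 1,125 mg.
- Level 2: 90 / (1 × 90) = 100%; delivered 90 × 6.25 = 562.5 mg.

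The score is the same and the dose is half (6.25 / 12.5 = 50%). In the as-treated model both patients enter as 1.

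**2. Arm-level effect.** Let *a* be the share of prescribed pills taken and *f* the share of the arm on level 2. Measured adherence is *a*, whatever *f* is. Mean delivered dose as a share of target is *a* × [(1 − *f*) + 0.5*f*]. The documents give no value for *f*, so the shares below are assumptions; *a* = 0.9 matches the plan's placebo adherence.

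| *f* | Measured adherence | Delivered dose, % of target |
|---|---|---|
| 0% | 90% | 90% |
| 20% | 90% | 81% |
| 30% | 90% | 76.5% |
| 50% | 90% | 67.5% |

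Even with half the carvedilol arm on level 2, the adherence comparison with a 90% placebo arm would show no difference from this cause.

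**3. Withdrawals.** Only voluntary withdrawals are compared. A patient held at level 2 is not a withdrawal. A patient removed for failing level 1 to level 2 leaves by protocol rule, so need not count as voluntary either.

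**4. What the other analyses catch.** Set the reasons in Section 4.3.1 for not escalating beside the capture rules:

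- Grade 2 dizziness or flushing: counts as a Grade 2-4 toxicity if attributed probably or definitely to study drug (Section 13.4).
- Clinically significant ECG changes: to be documented as an adverse event (Section 10.6.2), with no grade stated.
- Systolic pressure below 90 mmHg or heart rate below 50: not tied to any grade, so an asymptomatic case may never enter the toxicity test.
- Investigator judgement (Sections 4.3.1 and 4.3.3): no grade required.
- Symptom logs: taken at Days 14 and 42, when escalation is decided. Whether symptoms after the first level 3 dose in clinic enter the Day 42 log is not stated. Later logs from held patients describe the lower dose.

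**5. The plan's power figures, reproduced.** Exact enumeration of Fisher's test, two-sided 0.05:

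- Toxicity (Amendment #4): 91 × (1 − 0.38) = 56 per arm; 5% v 24.7% gives 80.0%, as stated.
- Withdrawals: 91 per arm; 26% v 47% gives 81.0%, in line with the stated 80%.
- Adherence (90% v 70%): the repeated-measures method is not stated, so there is no unique check.

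**6. Power of a comparison of level reached.** Same method, 91 per arm. The placebo share is an assumption.

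| Placebo reaching level 3 | Carvedilol reaching level 3 | Power |
|---|---|---|
| 99% | 88% | 85% |
| 95% | 80% | 84% |
| 90% | 73% | 81% |
| 85% | 66% | 82% |
| 95% | 90% | 17% |

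The 95% v 80% row is a failure rate of 5% v 20%. The planned toxicity test at 56 per arm has 58% power for those same rates, and only if every failure is also recorded as a qualifying toxicity.

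**The case against.** The strongest reply is that tolerability is not left to pill counts. Section 9.3.3 plans a by-arm test of Grade 2-4 toxicities, and several reasons for holding a dose can feed it. If failure rates were 5% v 30% and every failure were recorded as a qualifying event, that test would have 93% power at 56 per arm (99.6% at 91). This stands as partial capture. If only half the excess were recorded (5% v 17.5%), power falls to 44% at 56 per arm (71% at 91), and the attribution and grade rules make incomplete recording likely for asymptomatic pressure or heart-rate findings.

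A second reply is that the aim names low-dose carvedilol, not 12.5 mg, and that Section 4.4 allows maintenance at level 2 or 3. Adherence to the prescribed level is then a coherent measure of the titrated regimen. That is fair, and the measure should stay. But the hypothesis names 12.5 mg per day, and a reader of the results needs to know how many patients received it.

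A third is that reaching level 3 is not a clean measure of intolerance. The criteria include an open investigator-judgement item, and an asymptomatic reading can block escalation. This also stands, and it limits how the comparison should be described.

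A reader might infer that many carvedilol patients will be unable to take the drug and that the plan would hide it. The documents do not support this. They give no expected share on level 2; Section 2.3.3 cites two single-arm studies in mild disease with no adverse events that required dose reduction; and patients held at level 2 are still taking the drug, only not at the target dose.

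**Conclusion.** The gap is real and limited. No analysis uses the dose level reached, and the adherence, as-treated and withdrawal measures cannot register a patient held at half the target dose. The toxicity, ECG and symptom data catch part of such intolerance, not all of it. The plan could therefore report no tolerability difference between arms that differ in how many patients could take 12.5 mg per day. How likely that is cannot be said: the size depends on the share held at level 2, and every share used above is an assumption. Only the 50% dose ratio and the 100% adherence score are fixed by the documents.

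The primary intention-to-treat comparison of LV T-D slopes is unaffected as a test; what suffers is its interpretation and the as-treated analysis. The point is worth correcting before analysis because it bears on a stated secondary aim and costs little.

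**What to change.** 1. In Section 9.3.4, add a secondary by-arm comparison, in all patients who start study drug, of the level reached at the end of up-titration: level 3, level 2, or off drug during titration. Fix the time point after the optional second attempt, about two weeks past Day 42. Apply Fisher's exact test to reaching level 3. Patients who stop during titration count as not reaching it, so all 91 per arm contribute.
2. Report that table beside the adherence and LV T-D results.
3. In the as-treated analysis, use adherence scaled to the 12.5 mg per day target as well as adherence to the prescribed dose.
4. Report reasons for non-escalation where they were recorded. Section 4.3.1 describes the Dose Escalation Form only as confirming that a patient about to be escalated shows none of the listed signs, so reasons for holding a patient may not be on file.

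The cost is wording, one table and one more secondary test. The level should be obtainable from dispensing records. The result needs a caveat that reaching level 3 mixes asymptomatic haemodynamic effect with symptomatic intolerance. Making it the main tolerability comparison would be a matter of preference and is not needed to close the gap. No change to dosing or escalation rules is implied.
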